9.4 Procedures for recording and reporting Serious Adverse Events

[figure not shown]
All serious adverse events will be recorded in the medical records and the CRF as well as in the trial database, from which a line listing of SAEs can be extracted for review. The line-listing of SAEs will be reported to the Sponsor once per year.

All SAEs (except those specified in section 9.5 as not requiring reporting to the Sponsor) must be recorded on a serious adverse event (SAE) form. The CI/PI or designated individual will complete the Sponsor's SAE form and the form will be preferably emailed to the Sponsor within 5 working days of becoming aware of the event. The Chief or Principal Investigator will respond to any SAE queries raised by the Sponsor as soon as possible.

Where the event is unexpected and thought to be related to the intervention, this must be reported by the Investigator to the Health Research Authority within 15 days.

Completed SAE forms must be sent within 5 working days of becoming aware of the event to the Sponsor
Email forms to [contact]

Flow Chart for SAE reporting (this simple flow chart is for single site trial, please amend in line with trial specific requirements)

9.5 Serious Adverse Events that do not require reporting (if applicable)

All SAEs will be reported to the Sponsor.

9.6 Unblinding (if applicable)

The allocation will be known to the participant, the trial manager, the research audiologist, and the research assistants delivering the intervention and carrying out the outcome assessments. As such we do not expect there to be any need for unblinding.

9.7 Reporting Urgent Safety Measures

If any urgent safety measures are taken the CI shall immediately and in any event no later than 3 days from the date the measures are taken, give written notice to the relevant REC and Sponsor of the measures taken and the circumstances giving rise to those measures.

9.8 Notification of reportable protocol violations

A reportable protocol violation is a breach which is likely to effect to a significant degree:

- (a) the safety or physical or mental integrity of the participants of the trial; or
- (b) the scientific value of the trial.

The Sponsor will be notified immediately of any case where the above definition applies during the trial conduct phase.

9.9 Reporting incidents involving a medical device(s) (if applicable)

Any adverse incident involving a medical device will be reported to the manufacturer of the device, in this case the hearing aid manufacturer. This is especially important where the incident has led to or, was it to occur again could lead to an event classified as serious (see section 9.1 for definition of SAE); these will be reported within 24h. Other minor safety or quality problems should be reported along with incidents that appear to be caused by human error.

Adverse incidents related to a medical device can be reported directly to the MHRA via the online system (www.mhra.gov.uk). Alternative contact details: Medicines & Healthcare products Regulatory Agency Adverse Incident Centre ([contact]; [contact]).

9.10 Trust Incidents and Near Misses

An incident or near miss is any unintended or unexpected event that could have or did lead to harm, loss or damage that contains one or more of the following components:

- a. It is an accident or other incident which results in injury or ill health.

- b. It is contrary to specified or expected standard of patient care or service.
- c. It places patients, staff members, visitors, contractors or members of the public at unnecessary risk.
- d. It puts the Trust in an adverse position with potential loss of reputation.
- e. It puts Trust property or assets in an adverse position or at risk.

Incidents and near misses must be reported to the Trust through DATIX as soon as the individual becomes aware of them.

A reportable incident is any unintended or unexpected event that could have or did lead to harm, loss or damage that contains one or more of the following components:

- a) It is an accident or other incident which results in injury or ill health.
- b) It is contrary to specified or expected standard of patient care or service.
- c) It places patients, staff members, visitors, contractors or members of the public at unnecessary risk.
- d) It puts the Trust in an adverse position with potential loss of reputation.
- e) It puts Trust property or assets in an adverse position or at risk of loss or damage.

10 Data management

10.1 Confidentiality

All data will be handled in accordance with the UK Data Protection Act 1998. The CRFs will not bear the participant's name or other personal identifiable data. Research identification numbers (Participant IDs) will be used to uniquely identify each participant.

10.2 Data collection tools and source document identification

Data will be collected on trial specific CRFs or data collection tools such as electronic CRFs.

Source data contained in source documents will be accurately transcribed on to the CRF. Examples of source documents are medical records which include audiometric reports and other clinical reports etc.

A source document list will be implemented prior to the start of the trial to identify:

- which data is to be recorded directly onto the CRF;
- which data is recorded firstly into source documents, such as medical notes, and then transcribed into the CRF; and
- which data is not to be recorded in the CRF but only recorded in source documents, e.g. participant questionnaires.

It is the responsibility of the investigator to ensure the accuracy of all data entered in the CRFs. The delegation log will identify all those personnel with responsibilities for patient identification, data collection and handling, including those who have access to the trial database.

10.3 Completing Case Report Forms

All CRFs must be completed and signed by staff that are listed on the site staff delegation log and authorised by the CI to perform this duty. The CI is responsible for the accuracy of all data reported in the CRF. Once completed the CRFs will be kept in secure and locked UCL premises.

10.4 Data handling

In the trial, participant data obtained as described in the Trial Procedures will be collected from patients in accordance with the patient consent form, patient information sheet and sections 8.1 to 8.3 of this protocol. The data will be collected in paper form and electronic format.

All data will be kept in strict adherence to Good clinical practice (GCP) guidance, which includes storing data in a locked cabinet in a locked room controlled by the Chief Investigator (or person designated by the CI according to trial delegation log) and destroying recordings after transcription. Data will be stored in a secure environment to industry standards and accreditation (SLMS Data Safe Haven - IDHS). Backups are made every night of all files created or modified since the preceding night's backup and kept on a backup server that is kept in a secure and fireproof location, separate from the main unit computers. UCL, as the trial Sponsor, is the data controller for this trial. There is a UCL disaster recovery protocol in place to restore lost data from a separate, secure archive.

Qualitative interview data will be collected and stored using digital audio recording (eg MP3) where interviewees permit. Physical data (e.g., digital audio-recordings, hand written field notes) will be kept until data is transcribed and checked to allow traceability and stored in a locked cabinet in a locked room. All data will be anonymised. All documents will be assigned version numbers which will be presented in headers and electronic filenames. We anticipate this to be in the format N.n, where N represents a new, approved or finalised version of a document and n represents draft versions prior to finalisation.

All documentary and transcribed data will be anonymised and imported into the latest version of the qualitative analysis software, currently NVivo 9, which allows the storing, coding and organisation of qualitative datasets. All data files will be kept as .txt or .rtf non-proprietary formats or as .pdf files. Electronic files will be password-protected. We will ensure that data is collected in accordance with the trial protocol and procedures through regular meetings between the CI and researchers. The CI will review the quality of interviews and field notes at regular points across the period of data collection to ensure they are of a high standard. Metadata will be consistent and transparent.

Data analysis will be undertaken by the TACT research team (as per trial delegation log), and as directed by the trial statistician and CI. The TACT research team will process, store and dispose of patient data in accordance with all applicable legal and regulatory requirements, including the Data Protection Act 1998 and any amendments thereto. The participant data will not be transferred to any party not identified in this protocol and are not to be processed and/or transferred other than in accordance with the patients' consent.

The electronic CRF and databases for the trial will be developed by the trial team using standard tools within a secure electronic environment. Once the trial and qualitative interviews finished and the databases locked, all trial documentation will be archived within UCL records office, to ensure documents are not mislaid, damaged or destroyed. This will be the responsibility of the Chief

Investigator and is part of Sponsorship by UCL. The content of each box will be listed and a unique reference number allocated to each file. Access will be restricted to the trial personnel.

The research data arising from this research will be made available to the scientific community in a timely and responsible manner. We are committed to long-term preservation, high quality data management and strengthening the provision for secondary data analysis. All data will be managed within UCL data protection policy and publications policy: www.ucl.ac.uk/platforms/informatics/data_sharing

11 Statistical Considerations

11.1 Primary Outcome

This pilot trial aims at establishing the feasibility of a full-size trial of the hearing aid intervention versus healthy ageing intervention in people with MCI. This future trial will be a scaled-up version of the present pilot, modified with any lessons learnt in the current trial. The pilot's primary objective is therefore to establish feasibility of recruitment, randomisation, retention, and the acceptability of the trial interventions as follows:

1. Recruitment and randomisation: Proportion of eligible participants who are randomised into the trial – expected value $\geq 50\%$.
2. Retention: proportion of participants who are followed for the 6 months of trial duration, and endpoint measures are obtained – expected value $\geq 80\%$.
3. Acceptability of the Hearing Intervention: proportion of participants allocated to the Hearing Intervention completing ≥ 2 intervention sessions – expected value $\geq 80\%$ of intervention group.

The Primary Outcome of the Remote Hearing Intervention sub-study (during COVID-19), in keeping with the overall TACT primary objective, will be the feasibility of the RHI, in terms of:

1. Recruitment: achieving $n=12$ participants
2. Acceptability of the RHI proportion of participants allocated to the Hearing Intervention completing $\geq 2/3$ intervention sessions – expected value $\geq 80\%$.
3. Retention: proportion of participants completing outcome collection – expected value $\geq 80\%$.

11.2 Secondary outcome(s)

The pilot will also establish other aspects of feasibility as secondary outcomes. The pilot will assess trial procedures, including whether the interventions and schedule of assessments are delivered as per randomisation allocation, and whether these are acceptable to participants, and whether the allocation to hearing aid intervention or healthy ageing intervention results in a difference in use of

hearing aids between arms at the end of trial follow-up, as well as the use of novel hearing screening procedures for more efficient recruitment in the future trial.

These secondary outcomes will be operationalised as follows:

- a) Evaluation of the deliverability and acceptability of the Hearing intervention, Healthy Ageing Intervention and the schedule of assessment for participants.
 - i. We will monitor completion rates of the interventions by recording the proportion of participants who completed each visit of the intervention, any refused or discontinued visits for the Hearing and Healthy Ageing Intervention, and any refused or discontinued tests and instruments from the schedule of assessments.
 - ii. For the Hearing Intervention, we will record the number of participants with hearing aid fitted within **3 months** (target: 80%) and reported side effects.
 - iii. Qualitative assessment of interventions and schedule of assessments: Researchers will also evaluate the experience of the hearing and healthy ageing interventions and of the schedule of assessments through qualitative assessments of trial participants and their communication partners. We will interview up to 24 participants and relatives about each intervention (involvement, practicality, acceptability) and about their opinion of the assessment until theoretical saturation is achieved. We will include both participants who have benefited from the intervention and those for whom it was not useful, to find out what helped and what could be better.

- b) Evaluation of the adherence to the intervention in terms of hearing aid use in the Hearing Intervention group and whether the control arm provides a meaningful comparison (i.e. where hearing aid use is in a much lower proportion). This will be assessed by hearing aid adherence based on data usage download from the hearing aids and self-report in the Hearing Intervention and Healthy Ageing Intervention arm (as participants in this arm may obtain hearing aids outside of the trial, through the NHS system or privately). We expect $\geq 70\%$ adherence in the Hearing Intervention arm and $\leq 20\%$ adherence in the Healthy Ageing Intervention arm. Hearing aid use will be defined as a minimum of 4 hours a day on average since last trial assessment (when at home and in usual health) as defined by data logging at 6 months (end of trial), based on the hearing aid with the highest average use (as each participant has two hearing aids). Self-reported hearing aid use may be employed if needed, for instance if no data-logging is available for a participant. The Statistical Analysis Plan will further specify the use of these measures. We will estimate and report the difference in hearing aid use at 6 months between the Hearing and Healthy Ageing arms to inform sample size estimates for the future trial. The expected value of the difference in daily hearing aid adherence between arms is expected to be $\geq 50\%$ difference between the Hearing Intervention and Healthy Ageing Intervention arms in the proportions of participants maintaining hearing aid use at 6 months (end of trial). Other data on adherence will also be recorded, to include the number of hearing aids lost by participants in the intervention arm.

- c) We will also pilot the use of improved technology for the assessment of hearing which, if valid and acceptable in our MCI population, could then be employed in the future trial for improved trial screening and recruitment. This technology includes hearing screening tools (Hearcheck screener and Shoebox audiometry, an iPad-based audiometric test that can provide a basic

audiogram with minimal supervision by a trained professional that does not need to be an audiologist) which we expect would be sufficient for accurate detection of participants for the main trial, relative to the current screening procedure of full assessment by trial audiologist in all participants, which is very time-consuming and resource intensive. This will be assessed through ROC analysis of HearCheck and Shoebox audiometry relative to gold standard full audiometric testing conducted by the trial audiologist.

The Secondary Outcomes of the Remote Hearing Intervention sub-study (during COVID-19), in keeping with the overall TACT primary objective, will include:

1. Evaluation of the deliverability and acceptability of the Remote Hearing intervention.
 - a. We will monitor completion rates of the RHI by recording the proportion of participants who completed each contact visit of the intervention, any refused or discontinued visits, and any refused or discontinued tests and instruments from the remote schedule of assessments.
 - b. Qualitative assessment of the remote intervention: Researchers will also evaluate the experience of the RHI and of the schedule of assessments through qualitative assessments of trial participants. We will interview up to 12 participants about the RHI (involvement, practicality, acceptability) and about their opinion of the assessment.

11.3 Sample size calculation

This pilot trial will assess the feasibility of proceeding to the future definitive RCT of sufficient duration to detect differences in cognitive changes between arms. The main feasibility questions that the pilot aims to answer are: (a) is the trial feasible, in the sense of resulting in sufficiently high recruitment, randomisation and sufficiently low dropout at 6 months; (b) is the Hearing Intervention deliverable and acceptable to participants; (c) estimate the difference in hearing aid use at 6 months between the Hearing Intervention and Healthy Ageing Intervention arms to inform sample size estimates for the future trial. We are including cognitive outcomes to assess their feasibility and acceptability, and to provide estimates including standard deviation to be used in the sample size calculation for the full trial. As a feasibility study, the current trial is not powered to detect differences in the cognitive outcomes between the arms. Therefore, only descriptive analyses will be performed using the data collected. No formal power calculation is necessary, and instead the sample size has been determined as to provide sufficient precision (sufficiently narrow confidence intervals) for trial estimates of recruitment and randomisation, dropout, acceptability of the intervention, and difference in hearing aid usage between arms, as detailed below.

With 76 randomised participants, we will achieve the following 95% confidence intervals (CI) for our expected estimates of recruitment, randomisation, dropout, acceptability of the intervention, and difference in hearing aid adherence between the Hearing Intervention and Healthy Ageing Intervention at the end of trial [88]:

1. Recruitment and randomisation of eligible participants with a MCI diagnosis from NHS community memory clinics. Target: 50% of eligible participants will be randomised; with n=76 recruited subjects the 95% CI would be [39-61].
2. Follow-up: target of 80% randomised participants with complete follow-up at 6 months,

95%CI with n=76 would be [71-89].

3. Acceptability of the Hearing Intervention: proportion of participants allocated to the Hearing Intervention completing ≥ 2 intervention sessions – expected value $\geq 80\%$ of intervention group, 95% CI with n=76 would be [71-89].
4. Difference in daily hearing aid adherence between arms: target of 50% difference between the Hearing Intervention and Healthy Ageing Intervention arms in the proportions of participants maintaining hearing aid use at 6 months (end of follow-up), 95% CI with n=76 would be [31-69].

Mean, proportions, differences in means and proportions with corresponding 95% confidence intervals will be calculated as appropriate for the cognitive scales and other trial outcomes, to inform the sample size calculation for a full scale trial.

Criteria for the decision of progression to the main trial

We judge that these confidence intervals provide acceptable ranges to inform continuation to the main trial. The final decision to “go” or “stop”, that is, whether to proceed or not to the main trial, will be taken by the Trial Steering Committee after the end of trial and with consideration of whether the trial has met its primary and secondary outcomes, as well as any lessons learnt during the pilot.

As a **guidance to this decision**, we anticipate that if the 4 endpoint estimates above in this section, as measured in the pilot trial, fall within their respective expected confidence intervals as detailed above, this will be a “go” signal for a full scale trial. If the endpoint estimates fall up to 10% below the lower limit of their target confidence interval (as detailed above in this section) we will consider whether modifications to the trial design to improve these endpoints would be sufficient to remediate these issues when proceeding to the main trail. If any of these endpoints fall below these minimal rates this will be a “do not progress to RCT” signal.

The Remote Hearing Intervention sub-study (COVID-19) will contribute to this decision by providing initial descriptive data and a qualitative assessment on the feasibility and acceptability of a remote version of the Hearing Intervention.

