11.4 Planned recruitment rate

To reach the target sample size of 76 randomised participants, and assuming recruitment rate of 50%, 152 potential participants will need to be approached during the 78 weeks of recruitment, or just under 2 potential participants per week.

The recruitment base will be five NHS London memory services, with 600 MCI patients per year (four times the screening target). Camden & Islington Memory Services alone exceed 1200 new patient referrals per year, of which 20% have MCI (or 240 people per year). We estimate that based on these five patient identification centres, the referral rate will be approximately six potential participants per week; two participants will be suitable and will agree to participate (one per research assistant). We conducted a small (n=12) feasibility study with similar but less restrictive inclusion and exclusion criteria as the proposed trial. This study recruited seven participants in four weeks, of which five had been confirmed to have untreated hearing loss and would have met inclusion criteria for the planned trial (1.25 potential participant per week), based on a single memory service, so the projected figures should be achievable.

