11.6.2 Primary outcome analysis

We will produce estimates and 95% Confidence Intervals for:

- Recruitment: Number of participants who will be randomised into the trial, divided by the total number of screened participants, expressed as percentage
- Retention: Number of participants that do not drop out before 6 month endpoint assessment, divided by the total number of randomised participants, expressed as percentage
- Acceptability of the Hearing Intervention: proportion of participants allocated to the Hearing Intervention completing ≥ 2 intervention sessions, divided by the total number of participants randomised to the Hearing Intervention.

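### The recruitment interval [39-61] in Section 11.3 takes the 76 randomised as its denominator; at the 50% target the denominator is 152 and the interval is [42-58]

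*Protocol*

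**What the plan says.** Section 11.1 defines the first primary outcome as "Proportion of eligible participants who are randomised into the trial", with an expected value of at least 50%.

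Section 11.3 makes no power calculation and justifies the sample size by precision. It introduces its list of intervals with "With 76 randomised participants, we will achieve the following 95% confidence intervals (CI) for our expected estimates". Item 1 of that list then reads "50% of eligible participants will be randomised; with n=76 recruited subjects the 95% CI would be [39-61" (per cent).

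Section 11.4 does the recruitment arithmetic separately: "To reach the target sample size of 76 randomised participants, and assuming recruitment rate of 50%, 152 potential participants will need to be approached".

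The progression guidance at the end of Section 11.3 uses the same intervals. Estimates that "fall within their respective expected confidence intervals as detailed above" are a go signal. The next zone is defined by "If the endpoint estimates fall up to 10% below the lower limit of their target confidence interval", and estimates below that zone signal not to progress. The Trial Steering Committee takes the final decision.

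**The concern.** The outcome is a proportion with the number randomised on top and the number eligible underneath. The 76 are the randomised participants, so they are the numerator. Item 1 nevertheless uses 76 as the sample size of the proportion. Both cannot be true: with 76 eligible and a 50% rate only 38 people would be randomised.

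If the figure only described precision, the slip would be harmless, because it makes the interval look wider than it will be. But the lower end of the interval is also a decision limit. One wrong n therefore places two boundaries on the first primary outcome: the go limit and, through the 10% margin, the limit below which the signal is not to progress.

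**Working it through.** **Inputs**
- Number randomised: 76 (Sections 5 and 11.3).
- Target proportion: 0.50 (Sections 11.1 and 11.3).
- Confidence level: 95%, taken as two-sided, z = 1.96.
- Denominator implied by the target: 76/0.50 = 152 (the same figure as in Section 11.4).

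**Reproducing the printed interval.** Wald formula: p ± 1.96·√(p(1−p)/n).

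With n = 76: 0.5 ± 1.96·√(0.25/76) = 0.5 ± 0.112, i.e. 38.8 to 61.2%. This rounds to the printed [39-61], so 76 was used as the denominator.

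**With the denominator that the outcome definition requires.**

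With n = 152: 0.5 ± 1.96·√(0.25/152) = 0.5 ± 0.079, i.e. 42.1 to 57.9%, or [42-58].

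| Method | n = 76 | n = 152 |
|---|---|---|
| Wald | 38.8–61.2 | 42.1–57.9 |
| Wilson | 39.0–61.0 | 42.1–57.9 |
| Clopper-Pearson | 38.3–61.7 | 41.8–58.2 |
| Wald, continuity-corrected | 38.1–61.9 | 41.7–58.3 |

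No method gives [39-61] at n = 152. The printed interval is √2 = 1.41 times too wide.

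**Does the stopping rule for recruitment rescue it?** Suppose recruitment runs until 76 are randomised and the number eligible is random (inverse sampling). The standard error is p·√((1−p)/76) = 0.5·√(0.5/76) = 0.0406, equal to √(0.25/152) = 0.0406. Under the exact negative binomial with p = 0.5, the 95% range for the number eligible is 129 to 178, so the observed rate ranges from 76/178 = 42.7% to 76/129 = 58.9%. That is close to [42-58] and not to [39-61].

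**Effect on the progression limits**
- Go limit: 39% as printed, 42% on the corrected interval.
- Floor of the intermediate zone: 39 − 10 = 29% against 42 − 10 = 32% if the 10% means percentage points; 0.9·39 = 35.1% against 0.9·42 = 37.8% if it is relative. The protocol does not say which.
- Distance of 39% from target: (0.39 − 0.50)/0.0406 = −2.7 standard errors.
- Exact binomial with 152 eligible and a true rate of 50%: the chance of an estimate below 39% is 0.4%; below 42% it is 2.1%. A 95% lower limit has a nominal 2.5%.
- With 76 randomised, 76/181 = 42.0% (41.99%, just under 42) and 76/194 = 39.2%. Any eligible count from 181 to 194 is therefore go as printed and in the intermediate zone on the corrected interval.
- If the true rate were 40%, the chance of meeting the go limit with 152 eligible is 58% at 39% and 33% at 42%.

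**The case against.** The case on the other side accepts the arithmetic and disputes how much it matters. It has five parts.

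1. **The rule is guidance.** The Trial Steering Committee decides, weighing secondary outcomes and lessons learnt as well, and a go signal looks at four endpoints together. An estimate between 39% and 42% would lead to considering modifications, not to stopping. This stands and limits the importance of the error.

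2. **The error is conservative for precision.** The true interval is narrower than stated, so the argument that 76 gives sufficient precision for this outcome is strengthened. This stands too.

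3. **A progression limit is a judgement.** The protocol says the team judges these ranges acceptable, and it claims no 2.5% error rate for the go rule. A limit of 39% against a 50% target is not wrong in itself. This also stands: what is wrong is the stated derivation, so 39% is too lax only against the protocol's own rule that the limit comes from the 95% interval.

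4. **Recruitment stopped early.** Section 2 reports 36 randomised with complete data before COVID-19. If about 36 were the final number (an assumption), a 50% rate gives 36/0.50 = 72 eligible and a Wald interval of 38.5 to 61.5%, close to the printed one. The agreement is a coincidence. Sections 2, 5 and 11.3 still plan 76, and item 1 ties its interval to 76. It does mean that tightening the limit now would come after the protocol has already described recruitment as confirmed, which is a reason to prefer the neutral form of the fix.

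5. **The denominator is worded differently in different places.** Section 11.1 says eligible, Section 11.4 speaks of people approached, and Section 11.6.2 has "Number of participants who will be randomised into the trial, divided by the total number of screened participants, expressed as percentage". The value 152 is therefore conditional on the 50% applying to whichever group is finally used. The wording needs to be reconciled, but every version gives a denominator larger than 76, so none supports the printed interval.

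**Conclusion.** The point holds. The interval [39-61] is calculated on the numerator of the recruitment proportion. For 76 randomised at the 50% target the denominator is 152 and the 95% interval is [42-58], with a half-width of 7.9 points where the protocol implies 11.2. By the protocol's own rule the go limit for this outcome is 42% and not 39%, and the floor of the intermediate zone moves from 29% to 32% (points) or from about 35% to about 38% (relative).

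The result assumes the Section 11.1 definition (randomised over eligible) and the planned 76 randomised; it does not depend on the interval method or on whether the number randomised or the number eligible is regarded as fixed. It should be corrected because a decision limit rests on it. The practical weight is modest: a 3-point shift in one of four guidance limits, with no effect on any comparison between arms or on the adequacy of the sample size.

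**What to change.** In Section 11.3, item 1, replace the interval with one for the right denominator, for example: *with 76 randomised of 152 eligible, the 95% CI would be [42-58]*.

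Then settle the progression limit in one of two ways:
- carry 42% into the guidance, with the floor of the intermediate zone at 32% if the 10% means percentage points; or
- keep 39% (and 29%) and state that these are chosen thresholds, not limits derived from a confidence interval. Given that recruitment results are already described in Section 2, this is the safer choice unless the change can be shown to be independent of them.

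In the same edit, say whether the 10% is absolute or relative, and use one denominator (eligible, approached or screened) throughout Sections 11.1, 11.3, 11.4 and 11.6.2. If the interval is meant to describe the number actually randomised and not the planned 76, say so and give that number.

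The cost is one line in Section 11.3 and the matching limit in the guidance. No change to design, visits or sample size is needed. The stated precision improves; under the first option the go limit becomes slightly stricter.
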